1 PROTOCOL SUMMARY

1.1 SYNOPSIS

Title:	Adalimumab in Juvenile Idiopathic Arthritis-associated Uveitis Stopping Trial (ADJUST)
Study Description:	Multicenter, block-randomized, double-masked, placebo-controlled trial to compare the safety and efficacy of stopping adalimumab treatment versus continuing adalimumab treatment in patients with uveitis associated with juvenile idiopathic arthritis (JIA) or patients with chronic anterior uveitis (CAU). 118 patients with JIA-associated uveitis or CAU, with control of ocular inflammation on adalimumab will be randomized to either continue adalimumab at their current dose or stop adalimumab. Patients will complete monthly visits for 4 months in addition to visits at 6, 8, 10, and 12 months.
Objectives:	Primary Objective: To compare time to recurrence of ocular inflammation between patients with JIA-associated uveitis or CAU, randomized to stop adalimumab treatment and patients randomized to continue treatment. Secondary Objectives: To determine predictors of JIA-associated uveitis or CAU disease recurrence. To compare 6- and 12-month outcomes between the two treatment groups.
Endpoints:	Primary Endpoint: Time to treatment failure, up to 12 months post-randomization.

[figure not shown]
Study Population:	118 patients ≥2 years of age in the U.S., UK, and Australia, with a history of JIA-associated uveitis or chronic anterior uveitis. Original diagnosis must have been made prior to 16 years of age (but patients can be >16 at time of enrollment). Patients must have achieved steroid-sparing control of ocular inflammation and inactive arthritis on adalimumab or a biosimilar of adalimumab for ≥12 consecutive months. Patients may not have used systemic corticosteroid or ocular corticosteroid injection within the last 180 days and must be on ≤2 drops daily of 1% prednisolone acetate with stable dose for ≥90 days. The dose of adalimumab must be stable for ≥180 days and should be no greater than 40mg biweekly for patients ≥30kg and 20mg biweekly for patients <30kg. If on a concomitant antimetabolite, dose must be stable for ≥90 days and ≤25mg weekly for methotrexate, ≤3g daily for mycophenolate mofetil, ≤250 mg daily for azathioprine, or ≤ 20 mg daily for leflunomide.
Phase:	IV
Enrollment Centers:	10 centers in the U.S., 9 in the UK, and 1 in Australia. Additional sites may be added during the study to facilitate enrollment.

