3.1 TREATMENT FAILURE

Patients can discontinue the study treatment due to lack of efficacy and be declared a treatment failure if they have recurrence of ocular inflammation and/or recurrence of joint inflammation that is persistent and severe enough to necessitate unmasking to manage the arthritis recurrence.

Ocular inflammation is defined as ≥ 2 -step increase in AC cell from baseline, observed at 2 consecutive visits at least 7 days apart; $>0.5+$ AC cell for ≥ 28 days; $\geq 3+$ AC cell at a single visit; or $>0.5+$ vitreous haze, active retinal/choroidal lesions, or macular edema at a single visit.

Macular edema is defined as central subfield thickness on OCT > 2 standard deviations above normal thickness ($>320\mu\text{m}$ on Spectralis or $>300\mu\text{m}$ on Zeiss or Topcon) and having a greater than 20% increase from baseline *and/or* presence of intraretinal or subretinal fluid.

Patients with ocular inflammation that meets one of the treatment failure thresholds should return for an evaluation to evaluate whether the increased inflammation is sustained (called the Treatment Failure visit), as close to the 7- or 28-day period as possible, but no earlier.

Criteria for recurrence of ocular inflammation (at least one of the following in at least one eye)

Parameter	Definition
Anterior chamber cells*	≥ 2 -step increase** at two separate visits ≥ 7 days apart $>0.5+$ cell observed for ≥ 28 days $\geq 3+$ cell observed at a single visit
Vitreous haze***	$>0.5+$ haze at a single visit
Choroid & retina	Active retinal / choroidal inflammation and/or macular edema in either eye at a single visit. Macular edema is defined as central subfield thickness on OCT > 2 standard deviations above normal thickness ($>320\mu\text{m}$ on Spectralis or $>300\mu\text{m}$ on Zeiss or Topcon) and having a greater than 20% increase from baseline and/or presence of intraretinal or subretinal fluid

*SUN criteria; **increase is based on inflammation at baseline⁶⁰; ***NEI vitreous haze grading scale⁶¹

Patients who meet the treatment failure threshold of ocular inflammation at Month 12 will be re-evaluated after the Month 12 visit to assess for sustained inflammation which would result in treatment failure. If inflammation is sustained at the follow-up visit, then treatment failure is declared. At this point, patients and doctors will be unmasked, and doctors can treat per best medical judgement.

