Patients in the placebo arm will be encouraged to restart adalimumab. The date of treatment failure is defined as the date of the initial visit when the ocular inflammation reached the threshold. A minimum of 90 days of follow-up is required following treatment failure, so if treatment failure is declared with fewer than 90 days remaining in the 12-month follow-up period, follow-up may be extended to up to 15 months. Regardless of the course of treatment pursued after treatment failure, all patients will be followed through Month 12 or a minimum of 90 days, whichever is longer.

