Alternative models with interaction: tests of heterogeneity of effect. Consistency of effect between countries will be investigated. We propose to examine **homogeneity of treatment effect across countries** (by fitting survival models including country as a fixed effect along with treatment-country *interactions*). For the primary model and the aforementioned additional analyses of the primary

model, each will be repeated with an interaction term for country. All such analyses will be made available.

- As a sensitivity analysis, we will exclude treatment failures due to persistent and severe arthritis recurrence and assess the primary model with the recurrence of ocular inflammation only.
- We will examine treatment effect modification by disease type (JIA-associated uveitis vs. CAU) by fitting survival models including disease type as a fixed effect along with a treatment by disease type interaction. A further sensitivity analysis excluding individuals with CAU will be conducted. We acknowledge that these additional analyses may have low power since the trial is powered for main effects (not interaction) and excluding CAU patients will reduce the sample size. These analyses will also be made available.
- **Per-protocol.** We will conduct and report a per-protocol analysis excluding patients who missed 20% or more of their study medication.
- Our design yields failure times at discrete study visits. Statistically, we consider the failure time to occur at the first visit at which it is documented. A sensitivity analysis will be conducted in which we **impute the failure time** at the midpoint of the interval beginning with the last non-failure visit and the first failure visit.

Planned Secondary Analyses

Rationale. The proposed secondary analyses are intended to provide additional scientific information not present in the primary outcome and its analysis. These are of the following types: (1) use of the same outcome variable as the primary outcome, but at (a) different time points or (b) modeled by different covariates, and (2) use of different outcome variables.

- **The time to treatment failure, with censoring at 6 months**, a time to event outcome, will be analyzed using the template in the Primary Analysis above. This is the same outcome as for the primary outcome variable, except with observations restricted to 6 months.

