Analysis following the interim. Given the DSMC's decision on February 14, 2024 to stop enrollment but continue follow-up, a Cox proportional hazards regression for time to regaining control after treatment failure will be conducted as not all patients had reached month 12 at the interim. Two outcome variables for regaining control will be part of the planned analyses: time to initial control and time to sustained control. Time to initial control is defined as the first instance of meeting control criteria (as defined in Section 2.3.3) following the declaration of treatment failure. Time to sustained control is defined as the first instance of meeting control whereafter control is maintained through their month 12 visit, as it is possible that patients who experience failure will regain control, but then flare again. At the interim, participants who had experienced treatment failure will be included in the time to initial control analysis. Only patients who experienced treatment failure and had completed their month 12 visit by interim will be included in the time to sustained control analysis. When 12 month follow up is complete for all patients, all patients can be included in the pre-specified sustained control analysis.

Planned Secondary Analyses

Continuous outcome variables and binary outcome variables will be examined on an intent-to-treat basis in a similar way as indicated in Specific Aim 1. The following are planned analyses:

- **The BCVA at 6 and 12 months**, a continuous outcome,
- **The proportion of people exhibiting an arthritis flare during the first 6 months and during the first 12 months**, a binary outcome
- **The CHAQ score at 6 and 12 months**, a continuous outcome.

Planned Subsidiary Analyses

We propose to conduct the primary analysis and planned secondary analyses (as described above) using the subgroup of people who were randomized to discontinue adalimumab, subsequently had treatment failure, and then restarted adalimumab. We

will also conduct exploratory analyses to find predictors of reestablishing control of inflammation. The exploratory procedures described in Specific Aim 2 will be used (including descriptive tabulations, graphical exploration, and model selection using LASSO or other procedures). As before, exploratory analyses will always be labeled as such, and all analyses conducted will be reported.

Using procedures analogous to those in Specific Aim 1, we will also examine on an intent to treat basis:

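### Time to regaining control is dated at the first controlled visit on a 4- to 8-week visit grid with no interval-censored analysis, so short recoveries will be reported as about 7 to 8 weeks

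*SAP*

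**What the plan says.** SAP 3.1.3 (Specific Aim 3, Analysis following the interim) says that "a Cox proportional hazards regression for time to regaining control after treatment failure will be conducted". Two outcomes are defined. "Time to initial control is defined as the first instance of meeting control criteria" (those of SAP Table 2) "following the declaration of treatment failure". Time to sustained control is the first such instance after which control holds through Month 12. No covariates, interval handling or explicit day 0 are given.

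The examination calendar is fixed from randomization: "Patients will complete monthly visits for 4 months in addition to visits at 6, 8, 10, and 12 months" (Protocol 1.1). The Schedule of Activities (Protocol 1.3) puts these at weeks 4, 8, 12, 16, 24, 32, 40 and 48. Patients stay on this calendar after failure. The only added visit is one at 90 days, for failures with fewer than 90 days of follow-up left (Protocol 1.3 and 4.4).

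For the primary outcome, SAP 3.1.1 recognises the problem: "Our design yields failure times at discrete study visits". It adds a sensitivity analysis that places failure "at the midpoint of the interval beginning with the last non-failure visit and the first failure visit". Nothing similar is planned for time to control.

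**The concern.** Table 2 requires anterior chamber cell, vitreous haze and macular findings, so control is observed only at an examination. All that is known is that it returned between the last visit not meeting Table 2 and the first visit meeting it. An ordinary Cox regression with the later visit as the event time treats an interval 4 to 8 weeks wide as an exact date. If recovery usually takes less time than the gap, the reported time mainly measures the gap.

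The outcome has some weight. Protocol 4.1 hypothesises that anti-adalimumab antibodies go with a longer time to regaining control after restarting, Protocol 6.5.1 names regained control as of interest for Aim 3, and the SAP revision history says the analysis was added on the DSMC's recommendation. A median time to control from this trial would be read as the time patients take to recover.

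**Working it through.** **Inputs.** Visit weeks are from Protocol 1.3. Median times to failure of 10 weeks (stop) and 20 weeks (continue) are from SAP 3.3.1. True time to control is not in the documents; it is assumed exponential with medians of 2 to 8 weeks, equal in both arms. Confirmation visits are to be held "as close to the 7- or 28-day period as possible, but no earlier" (Protocol 3.1), so declaration is placed 0, 1 or 4 weeks after the threshold visit. Time is counted from declaration. The 90-day visit is included for failures first seen at week 40 or 48.

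**The plan's own figure.** The SAP states nothing for time to control. The failure medians do reproduce its sample size: with λ = ln2/10 and ln2/20, T = 48 and 88% power, its formula gives 52.9 per group, 105.8 in total, and 105.8/0.9 = 117.6, against 118.

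**Step 1: gap after failure.** A failure first seen at week 4, 8 or 12 has its next scheduled visit 4 weeks later. From week 16 the gap is 8 weeks. With S(t) = 2^(−t/m), the share of failures by week 48 first seen at week 16 or later is (S(12) − S(48))/(1 − S(48)):
- stop: (0.435 − 0.036)/0.964 = 41%
- continue: (0.660 − 0.189)/0.811 = 58%

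**Step 2: one case in full.** Stop arm, declared at the scheduled visit, true median 3 weeks, F(t) = 1 − 2^(−t/3), so F(4) = 0.603 and F(8) = 0.843.
- Recorded at 4 weeks: only failures seen by week 12 can be, 0.586 × 0.603 = 0.353.
- Recorded by 8 weeks: weeks 4 and 8 (share 0.441) × 0.843, plus week 12 (0.144; next visits are weeks 16 and 24) × 0.603, plus weeks 16 to 40 (0.387) × 0.843, which is 0.785.
- The recorded median is 8 weeks against a true 3.

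**Step 3: all cases.** Recorded median in weeks, stop / continue:

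| True median | Declared at visit | 1 week later | 4 weeks later |
|---|---|---|---|
| 2 | 8 / 8 | 7 / 7 | 4 / 4 |
| 3 | 8 / 8 | 7 / 7 | 8 / 8 |
| 4 | 8 / 8 | 7 / 7 | 8 / 8 |
| 6 | 8 / 8 | 7 / 11 | 12 / 12 |
| 8 | 12 / 12 | 11 / 12 | 12 / 12 |

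The stop-arm entry at 3 weeks with a 4-week delay is borderline: 50.0% are recorded by week 4.

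**Step 4: early against late failures** (first seen by week 12 against week 16 or later).
- Declared at the visit: 4 v 8 weeks for true medians of 2 to 4, and 8 v 8 at 6.
- Declared 1 week later: 3 v 7 at a true median of 2. At 3, exactly half of early failures recover within the 3-week gap, so the early median sits between 3 and 7. At 4 it is 7 v 7.
- Declared 4 weeks later: 4 v 4 at a true median of 2, and 8 v 4 at 3, which is a reversal.

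**Step 5: arm comparison.** With identical true recovery in both arms and Efron ties, the simulated stop-versus-continue hazard ratio for control is 1.01 to 1.08 for true medians of 3 to 8 weeks at the design failure medians. It is 0.98 to 1.13 if the continue-arm failure median is 60 weeks, and 1.03 to 1.06 with failure medians of 100 and 12 weeks. A repeat at the design medians gave 1.00 to 1.10 over the three declaration delays. At a true median of 2 weeks it was larger: 1.20, 1.17 and 1.05 for delays of 0, 1 and 4 weeks.

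**The case against.** The recovery time is assumed. Table 2 also requires topical steroid at no more than 2 drops a day, and Protocol 6.5.1 lets investigators restart or increase topical steroid after failure, so recovery under this definition may be slow. At a true median of 8 weeks the recorded 11 to 12 weeks is a smaller relative error. Visit windows of about 2 weeks either side, and any unscheduled examinations, would blur the grid. The SAP dates its primary outcome at the first documenting visit and treats interval handling as a sensitivity analysis, so a stricter rule for a descriptive, post-interim secondary analysis looks uneven. The interim was set at 34 failures, few for an interval-censored model. Aim 3's primary analysis, the proportion controlled at Month 12, is untouched.

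These points stand. They limit the size and priority of the problem and argue for keeping the Cox regression beside the new analysis. They do not answer the overstatement for short recoveries, because no planned analysis would reveal it.

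A reader might also infer two stronger points.
- That the same recovery is recorded as twice as long whenever failure is late. This holds only for short recoveries declared at, or about a week after, a scheduled visit. It disappears or reverses when declaration comes 28 days later, and for a fixed recovery of 5 to 8 weeks declared at a scheduled visit the late time (8) is equal to or shorter than the early one (8 or 12).
- That slower recovery in the continue arm is built in. Step 5 does not show a material effect except at very short recoveries, and SAP 3.1.3 does not say that this Cox model compares arms.

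**Conclusion.** The point holds as one about absolute times to initial control. If true median recovery is about 2 to 6 weeks, the planned analysis will mostly report 7 to 8 weeks and cannot tell these recoveries apart when failure is declared at a scheduled visit. At true medians of 3 to 4 weeks the overstatement is about 3 to 5 weeks over the declaration delays examined. The exceptions are a 2-week median with a 4-week delay (recorded as 4) and a 6-week median with a 1- or 4-week delay (recorded as 7 to 12).

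Bias in an arm hazard ratio is small, about 1.0 to 1.1 for true medians of 3 to 8 weeks. All of this rests on exponential recovery, equal in both arms, and examinations on the nominal weeks. Sustained control is dated in the same way, but the size of its error was not calculated.

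The time origin also needs settling. SAP 3.1.3 refers to declaration, whereas Protocol 3.1 states: "The date of treatment failure is defined as the date of the initial visit when the ocular inflammation reached the threshold". The two can differ by 7 or 28 days, which is as large as the recovery times in question. This is a worthwhile, inexpensive improvement to a secondary analysis and does not affect the primary result.

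**What to change.** In SAP 3.1.3:
- Keep the planned Cox regression.
- Add an interval-censored analysis of both control outcomes. The lower limit is the last visit not meeting Table 2 and the upper limit is the first visit meeting it (for sustained control, the first visit from which control holds). Use actual examination dates, including unscheduled ones. Show a Turnbull curve and fit an interval-censored proportional hazards or parametric model.
- Take any reported median time to control from this analysis, and say that precision is limited by visit spacing.
- State day 0 explicitly, as either the declaration date or the initial threshold visit.

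Midpoint dating alone is not enough: a recovery within the first gap would still read 2 weeks on the 4-week grid and 4 weeks on the 8-week grid.

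The cost is SAP wording and a different R routine, with no new data. Confidence limits will be somewhat wider and the interim data sparse, so the curve will be coarse until follow-up is complete. As the change comes after unmasking, it should be labelled so in the revision history, as the version 5 changes are.

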3.2 Transformations and model adequacy

3.2.1 Primary Analysis

We will assess the adequacy of the proportional hazards assumption using Schoenfeld residual plots, but supplement this with the Gill-Schumacher procedure and other graphical methods. Violations of the proportional hazards assumption will be reported, and will lead us to report additional analyses (the prespecified primary analysis will always be reported). We propose to report accelerated failure time models using the

same covariates, in the event of failure of the proportional hazards assumption.

3.2.2 Model validation and sensitivity

In all cases, standard statistical procedures will always be followed to ensure that no evidence indicates a violation of the assumptions underlying the statistical models used.

- We will assess the proportional hazards assumption for all Cox regressions using the methods given above (though we note that our primary hypothesis test is based on permutation).
- Also, we will examine Hosmer-Lemeshow goodness-of-fit tests for continuous predictors in binomial regressions. Linear models will always be assessed using residual plots (residuals vs. predicted values, and QQ plots), together with tests for normality (Anderson-Darling and Shapiro-Wilk procedures). Goodness of fit tests may be underpowered when they are needed the most (in small sample size studies). We do not propose formal thresholds for goodness-of-fit, but will add all such assessments to an analytic log, and make them available to the DSMC and statistical reviewers. Assessments of overdispersion will be conducted for count models.
- In the event of convergence difficulties in log binomial models we propose to use Poisson procedures with robust variance estimators. We propose to report the results of logistic regression in the event that all such procedures are unsuccessful. All such procedures will be reported.²²
- Jackknife influence estimates will be used in all analyses; single observations that could change the conclusions will always be reported; supplemental analyses dropping highly influential points will be reported at the discretion of the DSMC or statistical reviewers. We note that the presence of highly influential points does not invalidate the conclusions of a study, but such assessments contribute to the overall understanding of the trial. In our view, reporting the results of analyses dropping individual observations based on statistical outlier/influence tests *alone* is a dubious practice, in the absence of additional information about those outliers.
- Analyses in which our primary interest is in final outcomes (at either the 6 or 12 month timepoint for individuals who did not change treatment, or the time of failure for those who failed) will still be repeated using all available data (at all time points).

Failure of the modeling assumptions (such as normality) will result in conducting additional analyses. First, for continuous outcome variables, we will undertake normalizing or variance-stabilizing transformations of the outcome variable (such as power transformations). Second, we note that we are proposing use of permutation-based procedures for statistical testing whenever possible. Third, the use of bootstrap procedures, when applicable, will be considered in estimation of standard errors.

3.2.3 Missing covariates

Analyses using missing covariates will not apply to the primary analysis. In the primary analysis all individuals contribute observation time until censoring, and no covariates are expected to be missing. However, supplemental analyses of other outcomes, as well as the exploratory analyses in Aim 2, may necessitate treatment of missing data.

A complete case analysis will be used for all secondary analyses. If covariate data are missing for a large proportion of participants (>15%), we will also include a sensitivity analysis that uses regression-based multiple imputation (based on an assumption of missingness at random) to assess the impact of missing data on secondary outcomes of interest. We will use the `mice` package in R (Multiple Imputation with Chained Equations) with 100 replications to best impute the missing values. These sensitivity analyses may be used to determine the threshold value where imputation would change the overall findings (i.e., directly address the assumption of missingness at random). We note that Aim 2 is exploratory and hypothesis-generating.

Note that complete case analyses are, in general, biased, while imputation methods require an untestable assumption of missingness at random (or specific models of the nonrandom nature of missingness).

